# 1. PROTOCOL SYNOPSIS

Table 1

Protocol Title	The effects of dietary supplementation with a combination of flaxseed oil, borage oil and fish oil omega-3 fatty acids on ocular comfort including symptoms of dry eye.	
Protocol ID Number	SOVS2016-045	
Trial Classification	Evaluation	
Investigator(s)/Site(s)	Eye Research Group @ SOVS The University of New South Wales Sydney, Australia	
Overall Duration of Trial	1 year	
Number of Trial Participants Planned	138	
Planned Start Date	February 2017	
Primary Objective	To investigate the efficacy of a nutraceutical formulation (combination of flaxseed oil, borage oil and fish oil omega-3 fatty acids) on ocular symptoms including dry eye, compared to a placebo control.	
Secondary Objective	To evaluate the safety of a nutraceutical formulation (combination of flaxseed oil, borage oil and fish oil omega-3 fatty acids) over a 3 month period.	
Primary Safety Variable(s)	Visual acuity Biomicroscopy: ocular redness, corneal and conjunctival staining	
Primary Efficacy/Performance Variable	Subjective symptom scores measured using OSDI, OCI and DEQ-5	
Experimental design	 Retrospective  Prospective  Single group  Multiple group  Parallel group  Cross over  Contralateral	 Single masked (Trial Participant)  Single masked (Investigator)  Double masked  Sponsor masked  Open label  Other
Inclusion criteria	
 
▪ Able to read and comprehend English and give informed consent as demonstrated by signing a record of informed consent;
 
▪ Be at least 18 years old;
 
▪ Have symptoms of ocular discomfort as measured with the Ocular Surface Disease Index (OSDI) score of >12 at the Baseline visit;
 
▪ Willing to comply with the dosage and study visit schedule as directed by the investigator;
 
▪ No contact lens wear in the last 30 days and willing to refrain from contact lens wear for the duration of the study;
 
▪ No planned changes to diet and willing not to substantially alter their usual diet for the duration of the study, including their typical intake of fish;
 
▪ Willingness to notify the study investigator if instructed to alter their diet by health/medical practitioner;
 
▪ Willing to continue using any artificial tear supplements at the
 
	

	
same frequency throughout the study, as used prior to the study
 
 
▪ Have health and ocular health findings which would not prevent the participant from safely ingesting dietary supplementation with combination omega oils.
 
																								
Exclusion criteria	
 
▪ Any systemic disease that would preclude participants from safely ingesting dietary supplementation with combination omega oils;
 
▪ Self-reported allergy/sensitivity to any of the study product ingredients;
 
▪ Use of any polyunsaturated fatty acid-containing dietary supplements (such as fish oil, evening primrose oil, linseed oil) up to 12 weeks prior to the start of the study;
 
▪ Use of any of the following medications (including steroids) up to 12 weeks prior to start of the study or during the course of the study: 
 
○ Ocular medication, category S3 and above;
 
○ Any systemic or topical medications that will affect ocular physiology e.g. anti-acne medications such as Roaccutane and corticosteroid or immunosuppressant medications such as Hydrocortisone, Prednisolone and antihistamine medications such as Claritine;
 
 
 
▪ Any systemic disease that may affect ocular health e.g. Graves disease, and auto-immune diseases such as ankylosing spondylitis, multiple sclerosis and systemic lupus erythematosus;
 
▪ Epilepsy or history of migraines exacerbated by flashing, strobe-like lights;
 
▪ Eye surgery within 6 months immediately prior to enrolment for this study;
 
▪ Rigid or soft contact lens wearer, including orthokeratology in the last 30 days;
 
▪ Previous corneal refractive surgery;
 
▪ Pregnancy or breastfeeding;
 
▪ The Investigator may, at his/her discretion, exclude anyone else who they believe may not be able to fulfil the study requirements, or if it is believed to be in the participant's best interests.
 
																								
Formulae	
Test capsules (per capsule) – "Supplement"
 
 
Concentrated Omega-3 Triglycerides-fish	332 mg	
 
Equiv. Eicosapentaenoic Acid (EPA)	134 mg	
 
Equiv. Docosahexaenoic Acid (DHA)	66.8 mg	
 
Flax Seed Oil (Linseed Oil)	334 mg	
 
Equiv. Oleic acid	58.5 mg	
 
Equiv. Linoleic acid	58.5 mg	
 
Equiv. Linolenic acid	192 mg	
 
Borago officinalis seed oil fixed (Borage)	434 mg	
 
Equiv. gamma-Linolenic acid	95.5 mg	
 
 
Placebo control capsules (per capsule)
 
 
Polyethylene glycol 400	400 mg	
 
Oleic acid BP/EP	659 mg	
 
Propylene glycol	115 mg	
 
	Concentrated Omega-3 Triglycerides-fish	332 mg	Equiv. Eicosapentaenoic Acid (EPA)	134 mg	Equiv. Docosahexaenoic Acid (DHA)	66.8 mg	Flax Seed Oil (Linseed Oil)	334 mg	Equiv. Oleic acid	58.5 mg	Equiv. Linoleic acid	58.5 mg	Equiv. Linolenic acid	192 mg	Borago officinalis seed oil fixed (Borage)	434 mg	Equiv. gamma-Linolenic acid	95.5 mg	Polyethylene glycol 400	400 mg	Oleic acid BP/EP	659 mg	Propylene glycol	115 mg
Concentrated Omega-3 Triglycerides-fish	332 mg																								
Equiv. Eicosapentaenoic Acid (EPA)	134 mg																								
Equiv. Docosahexaenoic Acid (DHA)	66.8 mg																								
Flax Seed Oil (Linseed Oil)	334 mg																								
Equiv. Oleic acid	58.5 mg																								
Equiv. Linoleic acid	58.5 mg																								
Equiv. Linolenic acid	192 mg																								
Borago officinalis seed oil fixed (Borage)	434 mg																								
Equiv. gamma-Linolenic acid	95.5 mg																								
Polyethylene glycol 400	400 mg																								
Oleic acid BP/EP	659 mg																								
Propylene glycol	115 mg																								
Administration	
3 capsules per day, orally for 40 days. 2 capsules per day, orally thereafter for approximately 50 days.
																								
Human Research Ethics Committee Status /	
This trial requires Human Research Ethics Committee approval prior to study initiation, any advertising, and participant consent/enrolment.
																								

Regulatory Status	This trial requires approval from the Therapeutic Goods Administration.
--------------------------	---

## 4. BACKGROUND INFORMATION

### 4.1. Product

The normal tear film is a relatively stable, thin film composed of a superficial lipid layer and an aqueous layer intermixed with a mucous gel layer, which is partially adherent to the corneal and conjunctival surface epithelium. Dysfunction of one or more components of the tear film can lead to loss of tear film stability and symptoms of dry eye.

The chronicity of dry eye disease suggests that dysregulation of immune mechanisms leads to a cycle of continuous inflammation. Accordingly, because of better understanding of the inflammatory-mediated pathogenesis of dry eye disease, anti-inflammatory therapy is considered a causative therapeutic approach, since its objective is to interrupt the inflammatory cascade, rather than other treatment modalities aimed at providing symptomatic relief.

Essential polyunsaturated fatty acids omega-3 and omega-6 are the precursors of eicosanoids, which are locally acting hormones that mediate the inflammatory processes. There is good evidence that the consumption of oily fish has a protective effect against dry eye, and other studies have provided evidence of the beneficial effect of supplementation with omega-3 essential fatty acids in the treatment of dry eye disease.

However, there have been limited well designed randomised clinical trials published. Therefore, the purpose of this study is to conduct a randomised, placebo-controlled, double-masked study to investigate the effects of dietary supplementation with a combination of flaxseed oil, borage oil and fish oil omega-3 fatty acids on ocular comfort including signs and symptoms of dry eye.

### 4.2. Summary

#### 4.2.1. Risks and Benefits

##### **Risks of the Clinical Trial**

It is possible that participants may have an adverse reaction to ingesting the study product. Potential problems associated with ingesting nutraceutical supplements are likely to be gastric/digestive in nature.

Any untoward signs or symptoms will be treated by immediate discontinuation of use of the study product and participation in the study until all signs and symptoms have returned to normal. The participant will be referred for appropriate medical treatment if required.

Any potential participants with a self-reported allergy/sensitivity to any of the ingredients in the study product will be excluded from the study.

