## **7.3. Withdrawal and Follow-up Procedure**

Participants who are permanently withdrawn from the study should be seen as soon as possible after stopping use of the study product for a final visit to assess participant safety and to return any unused study product. This may be done at a routine clinic visit or an unscheduled visit if it occurs between routinely scheduled visits.

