### 7.3.1. The Final Study Exit Visit

Where possible, the data requirements for the final study exit visit are the same assessments as for the 3 month visit shown in Table 5. However, the minimum data requirements include:

- Visual acuity
- Slit-lamp biomicroscopy (ocular redness, corneal and conjunctival staining)

For withdrawal of consent, a 'Revocation of Consent' document should also be signed, if possible.

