#### 13.1.3. Analysis

Participants who have commenced the study treatment will be included in the analysis dataset. Reasons and frequency distribution of participants discontinued at Baseline will be reported. The analysis of efficacy variables such as subjective ratings will employ only scheduled and evaluable visits.

The analysis of safety variables such as adverse responses will include all visits, including all unscheduled visits.

Data will be summarised as means  $\pm$  standard deviations for variables measured on an interval scale and median  $\pm$  inter-quartile range for ordinal variables. Statistical tests will be employed to determine significant differences between between visits and  $p \leq 0.05$  will be considered statistically significant. Multiple comparisons will be adjusted using Bonferroni's correction. Commonly used tests of significance at each visit may include paired t-tests and group t-test for parametric data and Wilcoxon sign rank test and rank sum test for non-parametric data or repeated measures Analysis of Variance (ANOVA) for parametric data to determine differences between within-subject factors. Ranked variables will be analysed non-parametrically using Friedman's analysis of variance or Wilcoxon Signed Rank test to determine differences. Paired categorical variables will be compared using McNemar's test and grouped categorical variables will be analysed using Chi-Square tests.

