### **13.3. Accountability of Data**

Individual data points that are missing will be excluded from analysis involving only those specific variables. A participant's complete visit data will not be excluded if some of the observations are missing. Data from unscheduled visits will be used only for adverse response analysis. Inclusion of outliers in the analysis will be based on the magnitude of change in test statistic with and without the outliers. Outliers will preferably be retained unless there is significant change in test results.

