### HEALTH AND WELLBEING SURVEY

1. Since your last visit, have you:

- a) Been hospitalized? Yes / No
- b) Used any new medication or changed medication regimens? Yes / No
- c) Experienced any Gastrointestinal irritation e.g. diarrhea, heartburn, bloating or nausea? Yes / No
- d) Experienced unusual bleeding? Yes / No
- e) If you answered yes to any of the above, please explain:

---

---

---

---

2. On average, how many times per day did you ingest the study product during the past week?

---

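### Section 4.2.1 suspends study participation as well as product for untoward signs or symptoms, so a primary questionnaire score can be lost for tolerability reasons; the likely effect is small and cheap to avoid

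*Combined protocol and SAP*

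**What the plan says.** Section 4.2.1 (Risks and Benefits) deals with adverse reactions to the capsules. Untoward signs or symptoms are to be met by "immediate discontinuation of use of the study product and participation in the study until all signs and symptoms have returned to normal". Two things stop, product and participation, and both stops last until recovery.

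The primary endpoint (Section 6.1.6; instruments named in the Synopsis) is a set of symptom questionnaires: OSDI, OCI and DEQ-5. Table 4 schedules them at baseline, 1 month (±7 days) and 3 months (±14 days). The last of these columns is headed as both Visit 3 and study exit.

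For permanent stops, Section 7.3 says: "Participants who are permanently withdrawn from the study should be seen as soon as possible after stopping use of the study product". Section 7.3.1 adds that, where feasible, "the data requirements for the final study exit visit are the same assessments as for the 3 month visit", but it then sets a minimum of visual acuity and slit-lamp examination. The questionnaires are not in that minimum.

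On analysis, Section 13.1.3 states: "Participants who have commenced the study treatment will be included in the analysis dataset". The same section says that efficacy analyses "will employ only scheduled and evaluable visits". Section 13.3 states: "Data from unscheduled visits will be used only for adverse response analysis", and also: "Individual data points that are missing will be excluded from analysis involving only those specific variables".

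Section 12.5 follows an adverse response until it resolves or the person is referred. It does not mention the visit schedule.

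**The concern.** Stopping the capsules after a reaction protects the participant. Stopping the symptom questionnaires protects nobody, and it removes primary-endpoint data from a randomised participant for a reason connected with how well the capsules were tolerated. Loss of that kind cannot be assumed random, and an available-case analysis does not correct for it.

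The sections combine as follows. A participant who is still suspended when a visit falls due has no instruction to attend. If the stop becomes permanent, the participant gets one early exit visit, which may be cut to a set without the questionnaires. If the questionnaires are completed there but the visit is off schedule, they do not enter the efficacy analysis. Including everyone who started treatment in the analysis dataset does not help, because it cannot supply a score that was never collected or is ruled out of use.

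At stake are a small loss of power and a comparison in which some of the missing scores may depend on tolerability.

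**Working it through.** **1. The plan's own sample size.** Inputs (Section 13.1.1): OSDI difference 10, SD 20, two-sided alpha 0.05, power 80%, 10% drop-out, 69 per group.
- n per group = 2 × (1.960 + 0.842)² × 20² / 10² = 62.8, so 63.
- Allowing for drop-out: 63 × 1.1 = 69.3, or 63 / 0.9 = 70. The stated 69 per group (138 in total) is reproduced to within rounding.

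**2. When a suspension can cost a score.** One month is defined as 30 days (Section 6.1.4, Table 5); the windows come from Table 4.
- 1 month: 30 − 7 to 30 + 7 = days 23 to 37, which is 15 days.
- 3 months: 90 − 14 to 90 + 14 = days 76 to 104, which is 29 days.
- If the visit is assumed to be booked on day 30 or day 90, the rest of the window is 8 days (30 to 37) or 15 days (90 to 104).

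A score is at risk only if the stop covers the window, or what remains of it, or is never lifted. A shorter stop only moves the visit or reduces intake. The documents give no durations for these events.

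**3. How many people.** Section 12.4.1 lists stomach pain (<2%) and diarrhoea (<1%) as product risks.
- With no overlap, fewer than 3% are affected: 0.03 × 69 = 2.07, so about 2 in the supplement arm.
- This is an upper bound on score losses from the listed events, because step 2 shows that most events need not cost a score.

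**4. Effect on power.** Two-sample t-test, two-sided alpha 0.05, standardised difference 10/20 = 0.5. Retained after drop-out: 69 × 0.9 = 62.1, so 62 per arm.

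| Evaluable 3-month scores | Power | Change |
|---|---|---|
| 62 / 62 (losses already within the 10%) | 78.9% | none |
| 60 / 62 (2 further losses, supplement arm only) | 78.2% | −0.7 points |
| 60 / 60 (2 further losses in each arm) | 77.5% | −1.3 points |

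**5. If unlisted events add to this.** Heartburn, bloating and nausea are asked about in the Appendix II survey but have no stated rate. Assumed loss rates of 5% and 10% on top of drop-out, by the normal approximation (which gives 79.6% at 62.1 per arm with no further loss):
- 5%: 78.4% (one arm) or 77.3% (both arms).
- 10%: 77.1% (one arm) or 74.8% (both arms).

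**6. Possible bias.** If those lost differ from those retained by D points on the OSDI, an arm mean shifts by (fraction lost) × D. With D assumed to be 5 to 20, the shift at 3% is 0.15 to 0.6 points, and at 10% it is 0.5 to 2.0 points, against a target difference of 10. The documents do not say which sign D has.

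**The case against.** The case on the other side is substantial.

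- **The sentence is background text, and the stop is temporary.** Section 7.2 makes permanent discontinuation optional, Section 12.5 leaves it to clinical opinion, and Section 6.1.4 expects three visits from everyone. It is right that the stop ends on recovery, so a reader who inferred that every adverse reaction costs a primary score would go beyond the text. But the sentence is worded as an instruction, and no later section countermands it.
- **The plan expects people with such events to attend.** The survey at both follow-up visits asks whether, since the last visit, the participant has "Experienced any Gastrointestinal irritation e.g. diarrhea, heartburn, bloating or nausea". That covers those who have recovered or have attended anyway. It does not say what happens to someone still suspended on the due date.
- **There is already a rescue.** The Visit 3/exit column of Table 4 requires the questionnaires, and an exit visit may coincide with a routine one. This stands in part. It fails when an early exit is cut to the minimum set, or when it is unscheduled and so excluded from efficacy.
- **The return to normal might seem impossible**, since everyone enters with OSDI above 12. A reader might infer that suspensions could never end. In a paragraph about reactions to ingestion, the words most naturally refer to new events, so this reading is not relied on.
- **A larger power loss might be inferred** by applying 3% to all 138 (about 4 people) and placing all 4 in one arm. That would be 4/69 = 5.8%, which contradicts the rate of under 3% that produced the 4.
- **Pausing participation also spares a symptomatic person dyes and no-blink tests**, and Section 12.4.1 lists irritation from study procedures. This is correct, and it limits the fix to the questionnaires.

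**Conclusion.** The concern holds as a minor one. The protocol states a rule that, followed as written, can lose primary scores for tolerability reasons, and the exit and analysis rules do not fully recover them.

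The likely size is small: at most about 2 of 69 supplement participants from the listed events, and a power loss of 0 to 0.7 percentage points, or 1.3 if placebo loses as many. This rests on the listed rates with no overlap, on every such event costing a 3-month score (which overstates the loss), and on the plan's difference of 10 and SD of 20. Unlisted events could raise the count; the 5% and 10% figures are assumptions that show how far.

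A reader might infer that the result would be biased in favour of the supplement. The documents do not support that, since they give neither the split of losses between arms nor the symptom scores of those lost. Nor do they show that the trial's primary conclusion is in danger. The reason to act is that the loss is avoidable at low cost.

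**What to change.** 1. **Section 4.2.1.** Replace the phrase that suspends participation. State that product stops but that, unless consent is withdrawn, the OSDI, OCI and DEQ-5 are still completed at the 1- and 3-month dates counted from baseline. Dye tests, no-blink tests and other eye procedures are left to the optometrist while signs or symptoms persist.
2. **Sections 7.3 and 7.3.1.** Add the three questionnaires to the minimum exit set. Ask people who stop product permanently without withdrawing consent to complete the 3-month questionnaires as well. Without this edit, the single early exit visit would conflict with item 1.
3. **Section 13.1.3.** State that these scores count as scheduled and evaluable whether or not product is being taken. The section does not define evaluable, so off-product scores could otherwise still be dropped.
4. **Case report form.** Record the dates on which product is stopped and restarted.

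The cost is a minor amendment with co-sponsor and ethics committee approval (Section 15.1.3) and two date fields. Scores from people off product reflect less intake, so the observed difference may be slightly diluted. The safety stop of the capsules is unchanged.

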### **Benefits of the Clinical Trial**

Participants may experience reduced symptoms of ocular discomfort and dry eye during the study. However, there is no guarantee or promise that the participants will receive any health benefits from this clinical trial. The study product and participants' optometric care will be provided free of charge for the duration of the clinical trial.

### **4.2.2. Treatment Rationale**

Few studies have investigated the potential for nutraceutical dietary supplementation to impact ocular comfort, and to date, no controlled, randomised clinical trials have been conducted to evaluate the "supplement" nutraceutical formulation.

Therefore, the objective of this study is to investigate the effects of the "supplement" nutraceutical formulation (combination of flaxseed oil, borage oil and fish oil omega-3 fatty acids) on ocular symptoms including dry eye, compared to a placebo control.

### **4.2.3. Guidelines and Regulations**

The clinical trial will be conducted in accordance with the protocol, the Declaration of Helsinki (see Appendix 1), ICH GCP and local regulations as applicable including TGA and NH&MRC guidelines.

### **4.2.4. Trial Population**

138 participants will be enrolled.

## **5. STUDY OBJECTIVES AND CLINICAL HYPOTHESIS**

### **5.1. Study Objective**

The objective of this study is to evaluate ocular symptoms and signs when consuming the supplement nutraceutical formulation (combination of flaxseed oil, borage oil and fish oil omega-3 fatty acids) daily over a 3 month period, compared to a placebo control.

### **5.2. Clinical Hypothesis**

A greater reduction in ocular discomfort and/or signs of dry eye will be observed after daily consumption of the supplement nutraceutical formulation (combination of flaxseed oil, borage oil and fish oil omega-3 fatty acids) over a 3 month period compared to a placebo control.

## 6. STUDY DESIGN

This study will be a prospective, randomised, placebo-controlled, double masked study conducted over a 3-month period.

One hundred and thirty-eight (138) participants who meet the inclusion / exclusion criteria and give informed consent will be randomised to either the test capsules containing a combination of flaxseed oil, borage oil and fish oil omega-3 fatty acids ("supplement") or placebo capsules, identical in appearance, containing non-active ingredients polyethylene glycol (500mg), oleic acid (659mg) and propylene glycol (115mg) to be taken by mouth three times daily for 40 days and then two times daily for the remainder of the study, as per the manufacturer's guidelines. Every effort will be made to stratify enrolment by disease severity to ensure participants with mild, moderate and severe dry eye are represented in the study population. Stratification will be in a 2:2:1 fashion i.e. OSDI score >12 (55 participants), OSDI score >20 (55 participants) and OSDI score >45 (28 participants). Participants will be stratified according to dry eye severity prior to randomisation.

There will be a total of 3 scheduled study visits over a period of approximately 3 months - Day 1, 1 month and 3 months. Ocular comfort and symptoms of dry eye will be assessed via questionnaires. The tear film and ocular surface will be assessed using specialised instruments (slit lamp biomicroscopy, Lipiview, Vapometer and Oculus Keratograph) and stains. Safety will be assessed through measurement of visual acuity, ocular redness (eyelid and bulbar conjunctival redness), evaluation of the ocular surface using the slit lamp biomicroscope and the administration of a questionnaire to assess general health and wellbeing.

In addition, at the first visit only, body mass index and body fat composition will be measured to investigate the potential relationship between nutrition, body composition, and dry eye (Ho et al, Eye Contact Lens; Epub ahead of print 27 May 2016).

All proposed procedures conform to the NHMRC Statement on Human Experimentation.

Participants are considered enrolled when they have signed the informed consent form and are regarded as part of the clinical trial population.

